Observation plan - Synopsis

A multicentre, prospective registry to evaluate the safety and efficacy of minimally invasive ultrafiltration treatment and its effect on symptoms and rehospitalisation in patients with advanced volume overload

“GENTLE-UF REGISTRY”

Global registry on decongestion Therapy using Less invasive UltraFiltration

Study code:	UF-HF-01-INT
NCT No:	NCT02769351
Investigational device:	Chiara, peripheral ultrafiltration device
Protocol status:	English version V3.0
Date of current version:	22.12.2015
Sponsor responsible for study:	Fresenius Medical Care Deutschland GmbH [name] Germany

Observational Plan - Synopsis

Title:	GENTLE-UF REGISTRY: Global rEgistry on decongestioN Therapy using Less invasive UltraFiltration
Study code:	UF-HF-01-INT
Investigational device:	Chiara, peripheral ultrafiltration device
Aim:	In this prospective registry of the performance and safety of minimally invasive ultrafiltration, in some cases in combination with a post-hospitalisation disease management programme (in a subgroup of patients), treatment data will be collected using an electronic data recording system. The eCRF, which represents the clinical database, will be run on a server located in Germany and complies with current data protection regulations. It is intended to recruit about 300-500 patients with advanced volume overload at a minimum of 10 sites. The treatment data for each patient will be recorded over a period of 12 months. An interim analysis will be performed after 150 patients have been observed for 6 months. The aim of the registry is to expand the knowledge about ultrafiltration therapy in volume overload and to support the development of an evidence-based recommendation for routine clinical practice.

Endpoints:

Clinical endpoints

- Symptom status on discharge (NYHA class) after the first hospitalisation
- Weight change (time of 1st treatment until discharge from first hospitalisation); weight change metrically and weight loss categorially (yes/no)
- Rehospitalisation (yes/no) due to exacerbation of heart failure/volume overload of other origin within 12 months
- Unscheduled outpatient medical treatment for exacerbation of heart failure/volume overload of other origin (medical practice, outpatient department, emergency admission) within 12 months

Safety endpoints

- Significant deterioration of kidney function (on the basis of kidney retention parameters and eGFR)
- Significant electrolyte shift (serial measurement of electrolytes according to clinical requirements: sodium, potassium)

- Periprocedural (= emerging during the ultrafiltration treatment) symptomatic hypotension (yes/no)
- Periprocedural inotropic support required
- Events: related to venous access, apparatus-related, anticoagulation-related, UF procedure-related, unrelated
- Tolerability of treatment from the patient's perspective (subjective assessment on a 5-point scale)

Feasibility endpoints

- Successful treatments (duration of treatment defined at the discretion of the treating doctor and improved urinary output, no premature discontinuation)
- Successful peripheral accesses
- Need to change to another peripheral access (yes/no)
- Need to change to a central venous access (yes/no)

Performance endpoints

- Duration of UF therapy (in hours)
- UF flow rate in mL/h
- Total ultrafiltrate in mL/treatment
- Total ultrafiltrate in mL/hospitalisation

Other parameters

- Incidence of diuretic-resistant study participants
- Symptom status (NYHA) (during routine medical care, usually after 6 and 12 months)
- Changes in echocardiographic parameters (LVEF, LVEDD, LVESD, sPAD) (first hospitalisation, in the course of routine medical care (usually after 6 and 12 months), unscheduled hospitalisation)
- 6-minute walking test (on initial hospitalisation and in the course of routine medical care (usually after 6 and 12 months))
- Feasibility of home monitoring in a subgroup of patients at high risk of rehospitalisation (at the investigator's discretion)
- Home monitoring parameters (body weight, blood pressure, pulse, drug intake)
- Body water analysis by in-body device (body water composition [total body water, intracellular water, extracellular water], if device is available)
- Serial NTproBNP or BNP analysis (for recruitment, discharge after first hospitalisation, follow-up observation times in the course of routine medical care (usually 6 and 12 months), unscheduled hospitalisation)
- Anticoagulation regimen
- Oedema status (for times see Table 2)
- Diuretic dosage regimen (inpatient and outpatient)
- Regimen of guideline-adherent heart failure drugs (inpatient and outpatient)

Selection criteria:

- Age \geq 18 years
- Inpatient-treated patients with acute volume overload, preferably in association with cardiac decompensation with signs of incipient diuretic resistance (lack of increase in urine output despite significant escalation of diuretic therapy; e.g. \geq 80 mg furosemide / 24 h or $<$ 1375 mL urine output/40 mg furosemide per 24 h or equivalent dose of other loop diuretics [established clinically or from the medical history]).
- New York Association Functional Class (NYHA) III-IV at inclusion
- Systolic or diastolic cardiac dysfunction (HF-REF or HF-PEF)
- Adequate venous access (preferably peripheral arm vein) allowing a flow rate \geq 60 mL / min
- Written consent to the use of data in the registry (where necessary, by a legal guardian).

Exclusion criteria:

- Contraindication to anticoagulation (e.g. known heparin-induced thrombocytopenia, severe bleeding)
- Terminal renal failure (stage V, GFR $<$ 15 mL)
- Cardiogenic shock, e.g. in association with acute coronary syndrome (ACS)
- Other diseases or factors that, in the study doctor's opinion, constitute a potential contraindication to ultrafiltration
- Pregnant women, women in labour, breast-feeding women or women of childbearing potential, who are without adequate contraception or are planning a family. NB: a pregnancy test is performed systematically in women of childbearing age and the patient is not included in the event of pregnancy (positive test). It is absolutely essential that women, who have a negative test and who are included in the study, have an effective contraception.

Statistical analysis:

The aim of the GENTLE-UF Registry is to evaluate the safety and performance of a novel, minimally invasive ultrafiltration treatment.

The recorded data will be analysed using descriptive statistical methods. For metric variables (e.g. age), the following statistical parameters will be determined: number of valid data, mean, standard deviation and selected quantiles (minimum, 25% (lower quartile), 50% (median), 75% (upper quartile), maximum). With categorial variables (e.g. sex), absolute and relative frequency distributions will be calculated.

The effect of possible prognostic variables (e.g. age, sex) on the study parameters can be evaluated by means of subgroup analyses or statistical models.

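### The symptom endpoint is NYHA class at discharge without the entry class, so it only bounds the proportion improved and does not separate unchanged from worse

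*Combined protocol and SAP*

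**What the plan says.** The registry's title sets out to evaluate the treatment and "its effect on symptoms and rehospitalisation in patients with advanced volume overload". Under Clinical endpoints, the only symptom item is "Symptom status on discharge (NYHA class) after the first hospitalisation". It has no starting point and no definition of improvement.

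The next item in the same list is built differently: "Weight change (time of 1st treatment until discharge from first hospitalisation); weight change metrically and weight loss categorially (yes/no"). It has a start, an end, a metric form and a yes/no form. Under Other parameters, echocardiography is also listed as changes, BNP is measured from recruitment onwards, and the walking test is done during the initial stay.

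NYHA appears twice more:

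- Selection criteria: "New York Association Functional Class (NYHA) III-IV at inclusion". The class must therefore be assessed at entry.
- Other parameters: "Symptom status (NYHA) (during routine medical care, usually after 6 and 12 months"), again as a status.

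On analysis, the Statistical analysis section says: "With categorial variables (e.g. sex), absolute and relative frequency distributions will be calculated". It adds: "The effect of possible prognostic variables (e.g. age, sex) on the study parameters can be evaluated by means of subgroup analyses or statistical models". This second sentence permits further analysis but does not commit to any, and it does not name entry NYHA class.

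**The concern.** A question about symptoms in treated patients is a question about change: how many got better, stayed the same or got worse. A frequency table of discharge class answers that only where the discharge class alone settles the direction of change. With entry limited to III and IV, it does so for patients discharged in I or II. It does not do so for class III, which is one step better for a patient who entered in IV and no change for one who entered in III. Nor does it do so for class IV, which is no change from IV and a deterioration from III.

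The criterion admits both entry classes and does not fix their mix. Two sites, or two registries, could show the same discharge table after quite different symptom courses. The Aim section says that the registry should support an evidence-based recommendation for routine practice. A symptom result that cannot be read as change would be a weak basis for that, even for a purely descriptive statement.

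**Working it through.** The plan states no expected NYHA distribution and gives no derivation for its 300-500 patients, so there is no figure of its own to reproduce. The check asks what the discharge distribution alone can identify.

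**Inputs.** From the plan: entry class is III or IV (Selection criteria); the endpoint is discharge class (Clinical endpoints); the summary is by frequencies (Statistical analysis); recruitment is about 300-500 (Aim). All discharge shares and entry mixes below are assumptions, because the documents give none.

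**Notation.** Let a, b and c be the shares discharged in class I/II, III and IV, and q the share entering in class IV. Improved means better by at least one class.

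**Step 1: which cells are ambiguous.**

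| Entry | Discharged I/II | Discharged III | Discharged IV |
|---|---|---|---|
| III | improved | unchanged | worse |
| IV | improved | improved | unchanged |

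The first column is settled. The other two depend on entry class.

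**Step 2: bounds on the share improved.** The share improved is a plus the share that moved from IV to III.

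- Entry mix unknown: from a to a + b.
- Entry mix known, but not paired by patient: from max(a, q − c) to a + min(b, q).

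**Step 3: main example,** a = 40% (all class II), b = 60%, c = 0.

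- Entry mix unknown: 40% to 40% + 60% = 100%. The lower end is all patients entering in III, the upper end all entering in IV.
- Known 50/50 mix: lower max(40%, 50% − 0) = 50%; upper 40% + min(60%, 50%) = 90%.
- Same 50/50 mix, with the further assumption of an equal discharge split in both entry classes: 0.5 × 100% + 0.5 × 40% = 70%.

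A separate baseline table of entry class therefore narrows the range to 40 points but does not close it. Only pairing by patient does.

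**Step 4: other assumed splits.**

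| I/II, III, IV at discharge | Entry mix unknown | 20% known to enter in IV |
|---|---|---|
| 50 / 40 / 10% | 50-90% | 50-70% |
| 30 / 55 / 15% | 30-85% | 30-50% |
| 80 / 18 / 2% | 80-98% | 80-98% |

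The width is never more than the share discharged in class III.

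**Step 5: unchanged versus worse.** The share worse lies between max(0, c − q) and min(c, 1 − q). For the 50/40/10% split with q = 20%, that is max(0, 10% − 20%) = 0 to min(10%, 80%) = 10%. All or none of those discharged in IV may have worsened. In the Step 3 example nobody is discharged in IV, so this ambiguity does not arise there.

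**Step 6: after pairing.** The proportion is a single number with ordinary sampling error, 1.96 × √(p(1 − p)/n):

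| Assumed p | n = 300 | n = 500 |
|---|---|---|
| 0.5 | ±5.7 points | ±4.4 points |
| 0.7 | ±5.2 points | ±4.0 points |

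The bounds in Steps 3 and 4, by contrast, do not shrink as more patients are recruited.

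**The case against.** **The endpoint is not empty.** A reader might infer that it says nothing about how many patients improved. The documents do not support that. Because nobody enters below class III, the I/II share at discharge is a guaranteed minimum, and nobody discharged in IV has improved. If most patients leave in I or II, as in the 80/18/2% split, the remaining uncertainty is modest. This stands, and it limits the point to bounds.

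**The plan does not forbid the remedy.** A cross-table is itself a frequency distribution, and subgroup analyses and models are allowed. This is also true, but permission is not commitment, and entry NYHA class is not mentioned there. The later NYHA and walking-test values add information, but they do not link discharge class to entry class.

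**Only a synopsis is available.** The list of parameters refers to a Table 2 for assessment times, and neither that table nor the eCRF content is in the text. That III versus IV is stored for each patient is likely, given the criterion, but not confirmed.

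**Discharge timing.** A reader might infer that the assessment time is set by the outcome, since patients tend to go home when they are well enough. The documents state no discharge criterion and no length of stay, so this is plausible reasoning and not a documented defect. Variable timing would make sites less comparable, but it would not prevent counting the patients improved by discharge. An extra reading at a fixed time after the last treatment is not justified here. It adds an assessment to a registry whose later observations follow routine care, and its anchor is also clinician-decided, because the Feasibility endpoints leave treatment duration to the doctor.

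**Conclusion.** The point holds in limited form. As written, the symptom endpoint bounds the proportion improved and does not separate unchanged from worse. For an assumed 40% class II and 60% class III at discharge, the range is 40-100% with the entry mix unknown and 50-90% with a known 50/50 mix. Other assumed splits give wider or narrower ranges, and the size depends mainly on how many patients leave in class III.

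This is more than missing detail. The plan already treats weight as a change, the entry class is assessed for eligibility, and pairing the two classes alters what the registry can say on a question in its own title. The registry should make the change.

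The title's wording might lead a reader to take a paired result as an effect of ultrafiltration. It would not be one: the plan describes no comparator, so the table describes change and does not attribute it.

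**What to change.** 1. Under Clinical endpoints, define the symptom endpoint as change in NYHA class from inclusion to discharge from the first stay.
2. In Statistical analysis, specify an inclusion-by-discharge cross-table with the proportions improved by at least one class, unchanged and worse, given separately for entry class III and entry class IV.
3. Use the same table, from inclusion, for the NYHA values at about 6 and 12 months.
4. Report days from first treatment to discharge beside the NYHA and weight results, because time to discharge may differ between sites. That is an inference, but the figure lets the reader judge.
5. State that, without a comparator, these results describe change only.
6. Confirm that the eCRF records III versus IV at inclusion, and not merely that the criterion was met.

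The cost is a few lines of text and one table layout, provided that the entry class and the treatment and discharge dates are stored. If only eligibility is recorded, one eCRF field must be added, and patients already enrolled would need the class retrieved from their notes. No extra assessment is required.

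### The 12-month rehospitalisation rate has no rule for patients who die or are lost and no named mortality endpoint beside it, so it cannot be interpreted as planned

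*Combined protocol and SAP*

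**What the plan says.** All references are to the combined protocol and SAP, which is a synopsis.

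- **Endpoints, Clinical endpoints:** "Rehospitalisation (yes/no) due to exacerbation of heart failure/volume overload of other origin within 12 months". Unscheduled outpatient treatment for the same causes is listed over the same window.
- **Statistical analysis:** "The recorded data will be analysed using descriptive statistical methods". For items of this type, "With categorial variables (e.g. sex), absolute and relative frequency distributions will be calculated". A count of valid data is promised for metric variables only. No denominator is defined for the yes/no endpoints, and no time-to-event or competing-risk method is named.
- **Endpoints, all five lists** (clinical, safety, feasibility, performance, other parameters): death and mortality are not named. The nearest item, under Safety endpoints, is "Events: related to venous access, apparatus-related, anticoagulation-related, UF procedure-related, unrelated".
- **Aim:** "The treatment data for each patient will be recorded over a period of 12 months". Under Other parameters, some measurements are also listed at unscheduled hospitalisation, so readmissions may be captured as they occur.
- **Title and Statistical analysis:** the title names the effect on rehospitalisation, and the statistical section begins "The aim of the GENTLE-UF Registry is to evaluate the safety and performance".

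Nowhere does the text say how a patient who dies or is lost before month 12 is counted.

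**The concern.** Patients enter as inpatients in NYHA class III–IV, so death before any readmission is a foreseeable outcome. Someone who dies during the first hospitalisation can never be readmitted.

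A yes/no percentage needs a rule for such patients. They can stay in the denominator as *no*, or be left out as having no valid 12-month answer. Both fit the text, and they push the percentage in opposite directions as mortality rises. Two analysts following this plan could report different figures from the same data.

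If deaths are kept as *no*, a low rate may mean that patients stayed well or that they died first, and no named endpoint would tell these apart. The registry has safety as an aim and is meant to support recommendations for routine practice. No comparator is described, so a mortality figure would not prove benefit. It would show how many of the patients not readmitted were alive.

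**Working it through.** The plan states no event rate, power or precision, so there is no figure of its own to reproduce. Every rate below is an assumption, with constant hazards over one year and all patients at risk from the start.

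**Inputs.** Net readmission risk *r* (the 12-month risk if nobody died) 40%, range 30–50%. Mortality *m* 20%, range 5–30%. Loss *l* 5, 10 and 20%. N = 300 and 500, the ends of the recruitment range under Aim.

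**Step 1: two rules for death, no loss.**

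λr = −ln(1−0.40) = 0.5108; λd = −ln(1−0.20) = 0.2231; sum 0.7340.

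- Readmitted (deaths as *no*): (0.5108/0.7340) × (1 − e^−0.7340) = 0.6960 × 0.5200 = **36.2%**
- Alive and not readmitted: e^−0.7340 = 48.0%
- Died before any readmission: 52.0 − 36.2 = 15.8% (about 47 of 300 or 79 of 500)
- Died-first patients dropped: 36.2/(36.2 + 48.0) = **43.0%**

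The gap is 6.8 points. The 95% half-width, 1.96 × √(0.362 × 0.638/N), is 5.4 points at N=300 and 4.2 at N=500.

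**Step 2: vary mortality at r = 40%** (gaps from unrounded values).

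| Mortality | Deaths as *no* | Died-first dropped | Gap | Death or rehospitalisation |
|---|---|---|---|---|
| 5% | 39.1% | 40.7% | 1.6 | 43% |
| 10% | 38.1% | 41.4% | 3.3 | 46% |
| 20% | 36.2% | 43.0% | 6.8 | 52% |
| 30% | 34.2% | 44.8% | 10.7 | 58% |

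The columns for the two rules move in opposite directions. At 20% mortality, r = 30% gives 27.1% against 32.6%, and r = 50% gives 45.4% against 53.2%.

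**Step 3: one rate, two mortalities.** With deaths as *no*, solving for 36.2% gives:

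- 5% mortality: r = 37.1%, 4.0% die first, and 40.2% die or are readmitted.
- 30% mortality: r = 42.3%, 23.4% die first, and 59.6% die or are readmitted.

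The net risks were chosen to make the rates match. The example shows what the percentage cannot distinguish, not what is likely.

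**Step 4: loss, with deaths as *no* (true value 36.2%).** Let λc = −ln(1−l) and L = λr + λd + λc. Then the observed shares are R (readmitted) = (λr/L)(1 − e^−L), D (died first) = (λd/L)(1 − e^−L) and F (completed without event) = e^−L.

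At 10% loss, L = 0.8393, R = 0.3457, D = 0.1510 and F = 0.4320. Lost as *no* gives R = 34.6%. Lost left out gives R/(R+D+F) = 0.3457/0.9287 = 37.2%.

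| Loss | Lost as *no* | Lost left out |
|---|---|---|
| 5% | 35.4% (−0.8) | 36.7% (+0.5) |
| 10% | 34.6% (−1.6) | 37.2% (+1.0) |
| 20% | 32.9% (−3.3) | 38.4% (+2.2) |

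Over r 30–50% and mortality 10–30%, counting lost patients as *no* understates by 0.6–1.0, 1.1–2.1 and 2.3–4.3 points at 5, 10 and 20% loss.

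**The case against.** The strongest reply has four parts.

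1. **It is a synopsis.** Denominators and event definitions usually sit in a fuller plan, and a Table 2 is cited but not shown. This stands as a limit: what is shown is that the available text is silent. Table 2 is cited only for the timing of oedema status. If a rule exists elsewhere, citing it settles the part about counting.
2. **Deaths may already be captured** among the safety events, which include unrelated ones, and would then be tabulated. This also stands, so a reader should not infer that deaths go unrecorded. But a relatedness category is not a planned 12-month mortality figure.
3. **Counting deaths as *no* is legitimate.** With complete follow-up it equals the competing-risk cumulative incidence, so it is not an error in itself. It still falls as mortality rises and needs mortality beside it.
4. **The registry is descriptive and the effect may be small.** No hypothesis test is planned, so type I error and power are not at issue. At 10% mortality the gap between rules (3.3 points) lies inside the sampling half-width, and the loss bias at 5–10% loss is modest. A descriptive percentage nonetheless needs a denominator.

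A reader might also infer that the reported rate will fall as mortality rises. The documents do not support that: it holds only if deaths count as *no*, and reverses if patients who died first are dropped. The plan chooses neither.

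**Conclusion.** The concern holds in a limited form and should be fixed. The available text gives no rule for death or loss and plans no mortality figure, so neither the meaning of the 12-month rehospitalisation percentage nor its direction of movement with mortality is fixed.

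The death rule is the larger issue: 6.8 points between two admissible rules in the base case, more than sampling error at either end of the recruitment range, but less than it at 10% mortality. Loss is secondary, and becomes comparable with the half-widths only towards 20% loss and the upper end of the range examined.

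These sizes rest on assumed rates and constant hazards. The model does not treat in-hospital deaths separately. Confidence is moderate, because the source is a synopsis.

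**What to change.** - Name all-cause mortality, in-hospital and at 12 months, as a safety endpoint.
- Among patients discharged alive, report the 12-month cumulative incidence of first rehospitalisation for heart failure or volume overload by the Aalen-Johansen estimator, with death as a competing event and censoring at last contact. This states how deaths and losses are counted and replaces the plain percentage.
- Report mortality beside it, because this estimate also falls as mortality rises. Give the numbers who died, were lost and completed 12 months.
- Optional: the composite of death or rehospitalisation, and the same treatment for first unscheduled outpatient treatment.

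The cost is one endpoint line, a few sentences in the statistical section and slightly more analysis work. Event, death and last-contact dates are needed in the eCRF if not already captured; the eCRF is not shown. The sample size does not change. The estimate still assumes that loss is non-informative, which the report should say.

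### Does the yes/no endpoint on changing to central access, beside an undefined peripheral-success endpoint, hide how many patients were treated centrally?

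*Combined protocol and SAP*

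**What the plan says.** The access items stand together under Feasibility endpoints. After treatment success, which carries a definition in brackets, come three short entries: "Successful peripheral accesses", "Need to change to another peripheral access (yes/no" and "Need to change to a central venous access (yes/no". None of the three names a unit (access, treatment or patient) or a denominator, and the first gives no criterion for success.

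Under Selection criteria, entry requires "Adequate venous access (preferably peripheral arm vein) allowing a flow rate" of at least 60 mL/min. No exclusion criterion mentions central access.

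The product is described as "Chiara, peripheral ultrafiltration device". Under Statistical analysis, the aim is "to evaluate the safety and performance of a novel, minimally invasive ultrafiltration treatment". The analysis is descriptive, and for categorical variables "absolute and relative frequency distributions will be calculated". No alpha, power, margin or performance goal is given.

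Performance endpoints include ultrafiltrate per treatment as well as "Total ultrafiltrate in mL/hospitalisation", so more than one treatment per stay is foreseen.

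**The concern.** For a device presented as peripheral and minimally invasive, an obvious feasibility question is how many treated patients needed a central line at any time. The change endpoint is the only listed item that comes close to answering it, and a reader could take it as the answer.

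Read strictly, it is not. A patient who started centrally either gets the value no, the same as a patient whose peripheral access held, or drops out because there was nothing to change from. In both cases the central start leaves no trace in this endpoint. The discrepancy can go only one way: the change rate can fall below the share with any central use but cannot exceed it. That would flatter the device in a registry meant to inform routine practice.

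The undefined peripheral-success endpoint adds to the worry. Its value depends on whether it is counted per puncture, per treatment or per patient.

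**Working it through.** The plan states no access rate, so there is no figure to reproduce. The check has three parts.

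**1. Does the change rate differ from any central use?** Let c be the share starting centrally and s the change rate among peripheral starters. Both are assumptions; neither is in the documents.

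- Any central use = c + (1 − c) × s
- Change endpoint = s if central starters are left out, or (1 − c) × s if they are coded no
- Difference = c × (1 − s) or c, respectively

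With n = 300 (the lower end of the planned 300 to 500) and s = 20%:

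| c | Central starts | Peripheral starts | Changes | Any central use | Change rate, left out | Change rate, coded no |
|---|---|---|---|---|---|---|
| 0% | 0 | 300 | 60 | 60/300 = 20% | 60/300 = 20% | 60/300 = 20% |
| 5% | 15 | 285 | 57 | 72/300 = 24% | 57/285 = 20% | 57/300 = 19% |
| 10% | 30 | 270 | 54 | 84/300 = 28% | 54/270 = 20% | 54/300 = 18% |
| 15% | 45 | 255 | 51 | 96/300 = 32% | 51/255 = 20% | 51/300 = 17% |

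For c = 5 to 15% and s = 10 to 30%, the difference is 3.5 to 13.5 points (left out) or 5 to 15 points (coded no). A lower assumed change rate gives the same pattern. With s = 5% and c = 20%, there are 60 central starts and 0.05 × 240 = 12 changes, so any central use is 72/300 = 24% against a change rate of 12/240 = 5% or 12/300 = 4%.

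The algebra is sound, but the difference is a multiple of c and vanishes at c = 0. It is also not an error in the change endpoint. Changes and any central use are two different quantities, and the endpoint claims to measure only the first.

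**2. Do the documents suggest c > 0?** For: the entry criterion states a preference, not a requirement. Against: the preference can mean an arm vein over another peripheral vein; the device is labelled peripheral; and "Need to change to another peripheral access (yes/no" presupposes that the first access was peripheral. A central start is neither excluded nor expressly allowed. The text leaves c unknown and leans towards small or zero.

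**3. Does the unit of peripheral success matter?** As an illustration, suppose 80 of 100 patients succeed at the first access and 10 of the other 20 at a second. Then 90/100 = 90% succeed per patient and 90/120 = 75% per access. Both figures are correct for their own question, and a table that labels its unit removes the doubt. Nothing in the documents gives the direction or size of an effect in this registry.

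**The case for a change.** The best case for a change is that it costs almost nothing (one form field for first access type and a sentence of definition) and that in a descriptive registry the proportions are themselves the result, so categories and denominators matter. The entry list also uses the same wording of preference for cardiac decompensation, while the endpoints provide for overload of other origin, so a stated preference in this document does not look binding. If every patient does start peripherally, the extra field would simply confirm it.

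Part of this stands. No listed endpoint or parameter gives the first access type; the safety item on venous access counts events, not access type. Peripheral success is undefined, while the item directly above it is defined.

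It does not establish a fault in the plan. What is available is a synopsis that refers to a table not included in it and to an electronic case report form that we cannot see. A form able to answer the three access items would normally note which access was tried and used, although that is an inference. Absence from the synopsis list is not absence from the database.

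The suggested three categories (peripheral throughout, changed to central, central from the start) are not clearly better either. They do not say where to put a patient whose peripheral attempt failed before treatment began, or one treated peripherally first and centrally in a later session. They would replace one ambiguity with another unless attempted and used access were separated for each treatment.

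**Conclusion.** No change to the plan is called for. The undefined unit and the unlisted first access type are gaps in detail in a synopsis, of a kind analysts settle when they write the tables: state what counts as a successful peripheral access and per what unit, compute the change rate among patients in whom peripheral access was attempted, and, if any patient started centrally, print that count beside it. With the number of central starts and the number of changes both shown, any central use follows by addition.

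No size of effect can be given from the documents. It is zero if all starts are peripheral; the 3.5 to 15 points shown above rest entirely on assumed shares. No hypothesis or threshold depends on the figure. The conclusion assumes that the case report form or a fuller plan records the access used. If it does not, the number of central starts might not be recoverable. That is worth asking the sponsor, but the synopsis alone does not show it to be a defect.

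### The synopsis lists no confidence interval for any endpoint, so safety and feasibility rates would be reported as bare percentages, and zero events at the interim would read as 0%.

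*Combined protocol and SAP*

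**What the plan says.** The paragraph headed Statistical analysis opens with "The recorded data will be analysed using descriptive statistical methods". For metric variables it names "number of valid data, mean, standard deviation and selected quantiles", the quantiles being the minimum, quartiles, median and maximum. For the rest it states: "With categorial variables (e.g. sex), absolute and relative frequency distributions will be calculated". Neither list includes a standard error or a confidence interval. A closing sentence permits subgroup analyses or models for prognostic variables, with age and sex as examples. It mentions neither precision nor site.

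Under Aim, the design is given as "It is intended to recruit about 300-500 patients with advanced volume overload at a minimum of 10 sites", with this interim: "An interim analysis will be performed after 150 patients have been observed for 6 months". No expected rate, precision target or other rationale for the sample size is stated. The registry is intended to "support the development of an evidence-based recommendation for routine clinical practice".

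Many safety and feasibility endpoints are yes/no items or event categories, such as symptomatic hypotension during treatment, need for inotropic support, events by cause, and need to move to another or a central access. Others appear to be counted per treatment or per access: successful treatments, successful peripheral accesses, and ultrafiltrate volume per treatment.

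**The concern.** Judging the safety of a device treatment and supporting a recommendation both mean generalising beyond the patients observed. A percentage alone does not show how far the data allow that. The gap is widest when few or no events are seen, because 0% carries no indication of the rate that remains plausible. The same applies to feasibility: an access success rate from 150 patients and one from 500 would look alike on the page.

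The design does not fill the gap either. Because 300 to 500 comes without a precision argument, nothing tells the reader what uncertainty was thought acceptable.

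**Working it through.** **Plan's own figure.** There is none to reproduce. The range of 300 to 500 is given without an event rate, interval width or error level.

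**Inputs from the synopsis.** n = 150 (interim), 300 and 500 (planned range); at least 10 sites.

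**Assumptions, not in the synopsis.** Two-sided 95% level; illustrative event counts and rates; intraclass correlation (ICC) of 0.01 to 0.05; equal site sizes.

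**Step 1: zero events, patients independent.** The exact (Clopper-Pearson) upper limit is 1 − 0.025^(1/n).

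- n = 150: 1 − 0.025^(1/150) = 0.0243, or 2.4%
- n = 300: 1 − 0.025^(1/300) = 0.0122, or 1.2%
- n = 500: 1 − 0.025^(1/500) = 0.0074, or 0.7%

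**Step 2: a few events.** For x events in n, the lower limit is the 2.5% point of Beta(x, n − x + 1) and the upper limit is the 97.5% point of Beta(x + 1, n − x).

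- 3/150 (2%): 0.4% to 5.7%
- 3/300 (1%): 0.2% to 2.9%
- 5/500 (1%): 0.3% to 2.3%

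**Step 3: a high success rate, assumed 90%.**

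- 135/150: 84.0% to 94.3%
- 450/500: 87.0% to 92.5%

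**Step 4: how much site could matter (secondary).** Design effect DE = 1 + (m − 1) × ICC, where m is patients per site. An interval that allows for site is √DE times as wide as one that does not.

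| n | sites | m | DE at ICC 0.01 | DE at ICC 0.05 | √DE |
|---|---|---|---|---|---|
| 300 | 10 | 30 | 1 + 29 × 0.01 = 1.29 | 1 + 29 × 0.05 = 2.45 | 1.14 to 1.57 |
| 500 | 10 | 50 | 1 + 49 × 0.01 = 1.49 | 1 + 49 × 0.05 = 3.45 | 1.22 to 1.86 |
| 300 | 20 | 15 | 1 + 14 × 0.01 = 1.14 | 1 + 14 × 0.05 = 1.70 | 1.07 to 1.30 |
| 500 | 20 | 25 | 1 + 24 × 0.01 = 1.24 | 1 + 24 × 0.05 = 2.20 | 1.11 to 1.48 |

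At an illustrative 20% rate, the half-width 1.96 × √(0.2 × 0.8 × DE / n) with 10 sites goes from 4.5 points to between 5.1 and 7.1 (n = 300), and from 3.5 to between 4.3 and 6.5 (n = 500). The limits in Steps 1 to 3 contain no such allowance.

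**The case against.** **A descriptive single-arm registry needs no inference.** Descriptive analysis is acceptable here, and no hypothesis test is being asked for. An interval is compatible with description, and the stated purpose goes beyond describing the enrolled patients.

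**Readers can compute intervals themselves.** This stands in part. Counts, valid n and standard deviations are to be reported, so a simple interval can be worked out for any patient-level endpoint, including 0/150. For endpoints counted per treatment or per access, or to allow for site, published totals would not be enough.

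**The list is not exclusive, and this is a synopsis.** Also fair. The text does not say that nothing else will be produced, the optional models would normally yield standard errors, and a fuller plan may exist. The point is therefore that the synopsis does not specify intervals, not that it rules them out. The sentence on models is permissive, concerns prognostic variables and does not close the gap.

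**A tempting stronger reading.** A reader might infer that the plan overstates precision by ignoring site clustering. The documents do not support this: no precision is stated, so none can be overstated. Clustering becomes an issue only once intervals are added. Its size is also unknown. The ICC is assumed, 10 sites is a minimum, and the documents do not show that the endpoints vary strongly by site, although treatment duration, which is part of treatment success, is left to the physician. Nor do the documents give event rates or say that zero events would be taken as proof of safety.

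**Conclusion.** The point holds as a gap in the listed outputs: no measure of precision is specified for endpoints on which safety and feasibility conclusions will rest. It should be corrected, but it does not invalidate the design.

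The main size is that of the exact limits: with no events observed, a true rate of up to 2.4% at the interim, 1.2% at 300 patients or 0.7% at 500 remains compatible with the data. These limits rest on a two-sided 95% level and on independent patients.

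The site component is secondary and conditional. Under an ICC of 0.01 to 0.05 and exactly 10 equal sites, the design effect would be 1.3 to 2.5 at n = 300 and 1.5 to 3.5 at n = 500. It falls with more sites, and if the ICC is near zero it adds little. The missing interval stands as a point either way.

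**What to change.** Add to the Statistical analysis section, or confirm if a fuller plan already provides it:

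1. Two-sided 95% confidence intervals for the key safety, feasibility and clinical proportions and for mean weight change, at the interim and the final analysis. For proportions, use patient-level denominators and exact (Clopper-Pearson) limits, including for zero counts.
2. For endpoints counted per treatment or per access, a stated denominator and intervals that allow for repeated observations within a patient.
3. As a secondary sensitivity analysis, key results by site, with site-adjusted intervals where event counts allow (a random site effect, or cluster-robust with a correction for a small number of sites).
4. A statement that exact intervals for very low counts do not account for site.

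The cost is a few lines of text and minor programming, with no new data. The drawback is that reported results will look less precise.
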